6.5. Measures to Minimize Bias

6.5.1. Randomization

At screening, subjects will be assigned a subject identification number. When a subject is confirmed to be eligible for the clinical study, the subject will be randomized. Allocation of each subject to a given treatment will be done using a centralized electronic system (interactive voice/web response system [IXRS]). Subjects will be randomized in a 3:2 ratio to GLPG3970 or placebo.

6.5.2. Blinding and Unblinding

This is a randomized, double-blind clinical study. The subjects and the entire clinical study team, including the investigators, clinical study coordinators, and sponsor personnel are blinded to treatment assignment.

Blinded and packaged medication will be provided to the site. All IP formulations will be identical in appearance, shape, smell and taste, and will be packaged in the proper proportion to assure desired dosages and maintenance of the blinding.

The blind can be broken by the investigator for the safety of a subject. The investigator is encouraged to discuss considerations to break the blind with the sponsor's medical responsible, whenever possible and where the situation allows. However, the responsibility to break the treatment code in emergency situations resides solely with the investigator. The investigator is not required to discuss unblinding beforehand if he or she feels rapid emergency unblinding is necessary, but is required to inform the sponsor within 24 hours after unblinding has occurred.

The blind can be broken via IXRS by the investigator.

If the blind is broken for any reason during the course of the clinical study, the moment on which the blind was broken and all other relevant information will be documented by the site. The reason for breaking the blind will be indicated and justified in the source documentation.

If an AE leads to unblinding, the AE will be given as the reason for unblinding. All subjects who are unblinded should, where possible, complete the FU visit assessments 14±3 days after unblinding. Any AEs will be followed until resolution.

Code-breaking information (via IXRS vendor) will be provided to the bioanalytical laboratory responsible for plasma drug determination sample analysis, the person responsible for providing unblinded data to the Data Safety Monitoring Committee, the contract research organization (CRO) responsible for the population PK modeling, and to the sponsor pharmacovigilance vendor for SAE reporting purposes.

7. INVESTIGATIONAL MEDICINAL PRODUCTS

7.1. Identity of the Investigational Medicinal Product(s)

IP will be supplied to the pharmacist of the study site or to the hospital pharmacy, by and under the responsibility of the sponsor, who will also provide the investigator and pharmacist (or appropriate qualified member of the clinical study staff) with appropriate certificates of analytical conformity and European Union (EU) Qualified Person release documents.

For more details on the composition of the IP refer to the latest version of the IB and its relevant updates/addenda.

Detailed instructions on preparing and storing the IP will be provided to both the study site and the subjects.

7.2. Dosage and Administration

GLPG3970 will be provided as a powder and solvent to be reconstituted by the subject prior to use. The final dosage form for administration is an oral solution containing 400 mg of the active pharmaceutical ingredient G1567970 (G1567970 is the compound code for GLPG3970). A placebo powder and solvent for oral solution, to be reconstituted prior to use, will be also provided.

The IP needs to be taken q.d. at approximately the same time every morning on an empty stomach (i.e. IP intake should be at least 1 hour prior and at least 2 hours after a meal). At the baseline visit (Visit 1), IP will be administered on site after predose assessments have been completed. On visits 3, 4, and 5 subjects also need to take their IP on site. At Visit 1, 3, 5, and if applicable the ED visit, subjects need to come for the study visits in a fasting state (no food intake for at least 8 hours).

Subjects will receive powder and solvent to take home. The total content of the oral solution, reconstituted from the whole amount of powder and solvent, will need to be drunk. Detailed instructions for preparing and storing the applicable doses will be provided to the subject via on-site training on dummy kits and via a patient leaflet.

If a subject misses a dose (e.g. because he/she forgot to take the medication), he/she should take the missed dose within 12 hours after the planned intake time. If IP is not taken within 12 hours after the planned time, the missed dose should be skipped. For each dose taken at home, the time and date should be recorded in the subject's diary.

7.3. Packaging, Labeling and Distribution

IP packages will be labeled with clinical study-specific details, including storage conditions.

All manufacturing, packaging and labeling operations will be performed according to Good Manufacturing Practice for Medicinal Products and the relevant regulatory requirements.

Each medication kit will be identified with a unique kit number. Multiple kits can be provided to a subject at each visit, providing the subject with sufficient IP to cover the period until the next scheduled visit.

The distribution of IP to the site will only occur after the required local documentation is obtained, including clinical study approval by Competent Authorities and the IECs/IRBs, documentation on which the assessment of the investigator's qualifications was based (e.g. curriculum vitae), and the signed and dated study agreement and financial agreement.

To ensure study subjects maintain dosing per protocol requirements during this study special delivery services through DTP shipments of IP from the investigational site to the subject can be implemented in case of SARS-CoV-2 restrictions. DTP should only be used in case of emergency where on-site IP dispensation is not possible, and if allowed per local regulations. Local guidelines must be followed and regulatory approval or notification of authorities may be required. Agreement of the subject to receive IP at home is required prior to the shipment of IP from the investigational site to the subject's home. The DTP process used will be reviewed and approved by the sponsor, but the DTP shipments will be coordinated by the investigational site(s) in collaboration with the local CRO without the involvement of the sponsor to ensure clinical study integrity in case of SARS-CoV-2 restrictions.

7.4. Storage

Sites are to store IP supplies in a secure area until dispensed. Powder and solvent for oral solution at room temperature (below 30 °C), should not be refrigerated or frozen and protected from light and stored in the original packaging.

Sites will be required to monitor the storage temperature by using at least a min-max temperature-recording device and to keep a minimum to maximum temperature log, which must be completed each working day in order to establish a record of compliance with these storage conditions.

The investigator will instruct subjects on how the IP should be stored at home. Storage conditions to be taken into account by the subject when taking IP home, are described in the patient leaflet.

7.5. Treatment Compliance and Drug Accountability

The investigator should discuss treatment compliance with the subject prior to the start of the study. Missed doses should be discussed to try to ascertain the reason(s). Every effort should be made to ensure the proper subject dose. Subjects with poor compliance will be retrained by the site. IP administration as indicated by the subject (amounts as well as periods) will be recorded on the CRF.

The pharmacist or designated clinical study personnel will maintain a documentation of the total amount of IP received at site, amount dispensed to the subject, and the amount of IP returned by the subject to the site. IP supplies for each subject will be inventoried and accounted for throughout the clinical study. At the end of the treatment period, these records will be checked against the inventory by the study monitor. All clinical supplies will be stored in locked and access controlled facilities. Subjects will record IP administration at home in a subject diary.

Subjects will return any unused IP and empty IP packages at each study visit and/or ED visit. Upon sponsor approval, all unused IP and empty IP packages are to be returned from the sites and/or any vendor involved in the clinical study supplies management activities to the agreed location (depot), if possible. All returns and destruction must be properly documented.

8. CLINICAL STUDY ASSESSMENTS

Every effort should be made to ensure that CSP-required tests and procedures are completed as described in the Schedule of Activities (see Section 8.11). To avoid inter-observer variability, every effort should be made to ensure that all safety and efficacy evaluations are completed by the same individual who made the initial baseline determinations. In case study assessments are not performed for reasons related to SARS-CoV-2 pandemic restrictions, this should be documented in the medical records and e-CRF.

In case a randomized subject is not available to attend a scheduled study visit on site due to of SARS-CoV-2 travel restrictions, a phone call or a televisit may be conducted instead. It is strongly recommended to conduct planned study assessments for the applicable visit as per protocol as much as possible. If possible and if local regulations allow and the subject agrees, trained study staff or trained personnel are encouraged to collect study assessments at the study subjects' home or a local facility if social distancing and hygiene rules can be applied.

Only staff trained in conducting the protocol planned assessments are authorized to perform home or local facility visit assessments and the alternative arrangements need to be adequately documented. Direct to patient shipments are possible if needed. Subjects presenting with signs and symptoms of infection, including SARS-CoV-2 infection should immediately contact the site investigator, who should inform the sponsor's medical responsible as soon as possible, and SARS-CoV-2 testing should be performed.

8.1. Timing of Assessments

The study assessments will be undertaken at time points as specified in the Schedule of Activities in Section 8.11. At Visit 1, 3, 5, and if applicable the ED visit, subjects need to come for the study visits in a fasting state (no food intake for at least 8 hours).

ICF needs to be signed before any study procedure, including screening procedure, is carried out.

The sequence of study assessments will preferably be as follows when planned at the same time point:

1. Patient Questionnaires: Patients's Global Assessment of Disease Activity and Patient-Reported Functional Status and Pain
2. Investigator Questionnaires and joint counts
3. 12-Lead ECG
4. Vital signs
5. Blood sampling for clinical laboratory assessments and PK

The following collection time windows apply:

- 12-Lead ECGs, vital signs and physical examinations: within 3 hours predose.
- Urine sampling for clinical laboratory safety: any time predose, on the same visit day, and 2 hours postdose on visits 1 and 5.
- 
- Blood sampling for PK determination of GLPG3970:
 - Visit 1, 3, 4 and 5: within 30 minutes predose.
 - Visit 1: 1 sample within [0.5-1.5 hours postdose] and 1 sample within [2-2.5 hours postdose].
 - Visit 5: 1 sample within [4-6 hours postdose].
- 

8.1.1. Retesting During Screening

During the screening period, one retest of the following assessments is allowed:

- For resting pulse (after 5 min seated position).
- For re-evaluation of active joints and DAS28 score for defining moderate to severely active RA.

- For QuantiFERON –TB Gold test with indeterminate result (the subject is not eligible if retest result is indeterminate or positive).
- During screening or later during the study, retesting (resampling) of clinical laboratory safety tests or SARS-CoV-2 RT-PCR tests is allowed once, only for technical or transport reasons (e.g. sample hemolyzed, out of stability, late arrival at laboratory impacting sample quality, loss, or destruction of the sample before analysis).

8.1.2. Rescreening of Subjects

If a subject is a screening failure, it is allowed to rescreen the subject once, if the reason for failure is temporary and expected to resolve, as judged by the investigator. When a subject is rescreened, the subject needs to be reconsented and all screening assessments need to be repeated. The subject will be assigned a new subject identification number. The time in between 2 screening attempts could vary depending on the screening failure reason.

The following data will be collected for screening failure subjects: ICF signed data, demographics, failed inclusion or exclusion criteria, and AEs.

8.2. Unscheduled Visits

Additional visits can be performed at other time points for any safety assessments, if clinically indicated. These unscheduled visits and outcomes of additional assessments need to be recorded in the source and, if performed before the subject's last visit per CSP, also in the CRF.

8.3. Initial Subject and Disease Characteristics

Subjects will be asked to attend the study site for a screening assessment. After giving written informed consent, demographic data (year of birth, age, sex, ethnicity and race) will be collected and medical history will be taken, including RA disease history and treatment history. RA disease history will capture the duration of disease, clinical symptoms, and medication used to treat the disease. A physical examination will be performed, including measurement of weight and height. The subject's diagnosis of RA will be confirmed based on 2010 ACR/EULAR criteria (documented diagnosis) and classified as ACR functional class I-III.

Vital signs (systolic and diastolic blood pressure, pulse, oral/tympanic body temperature, the same method of measuring body temperature to be used throughout the study) will be measured and a 12-lead ECG will be recorded. Subjects should rest for at least 5 minutes in the supine position before the ECG recording, blood pressure and pulse measurement.

The inclusion and exclusion criteria will be checked to assess eligibility for the study. All screening tests will be reviewed to confirm eligibility before randomization and the first IP dose.

A serum pregnancy test will be done for all female subjects as well as an FSH test for postmenopausal female subjects.

8.4. Efficacy Assessments

8.4.1. Joint Counts

On the visits specified in the Schedule of Activities in Section 8.11 (see also Section 8.1, “Timing of Assessments”), each of 68 joints will be evaluated for tenderness (tender joint count, TJC68), and each of 66 joints will be evaluated for swelling (swollen joint count, SJC66) (Appendix 9).

A joint assessor with adequate training and experience in performing joint assessments will be designated at each study site to perform all joint assessments. The joint assessor should preferably be a rheumatologist, however, if a rheumatologist is not available, it should be a health care worker with at least one year’s experience in performing joint assessments. The assessor should remain the same throughout the study per subject, as much as possible. It is required that the designated joint assessor identifies an appropriate back-up assessor to provide coverage if the designated joint assessor is absent.

8.4.2. [REDACTED]

[REDACTED]

[REDACTED]

[REDACTED]

8.4.2.1. [REDACTED]

[REDACTED]

[REDACTED]

[REDACTED]

[REDACTED]

[REDACTED]

8.4.2.2. [REDACTED]

[REDACTED]

[REDACTED]

[REDACTED]

[REDACTED]

[REDACTED]

8.4.3. [REDACTED]

[REDACTED]

[REDACTED]

[REDACTED]

[REDACTED]

[REDACTED]

8.5. Safety Assessments

This section describes methods and timing for all safety assessments and recording. Additional assessments (e.g. unscheduled clinical laboratory tests or extra vital signs recordings) are allowed to ensure appropriate collection of safety data and to assess any perceived safety concerns.

8.5.1. Adverse Events

The AEs reporting period for safety surveillance begins when the subject signs the ICF and ends at his/her last FU visit.

Detailed definitions, ratings and reporting requirements for AEs and SAEs are found in Section 11.

8.5.2. Clinical Laboratory Evaluations

The following clinical laboratory safety tests will be performed:

- **Hematology:** hematocrit, hemoglobin, red blood cell count, white blood cell count, white blood cell differential count (absolute and relative), mean corpuscular volume (MCV), mean corpuscular hemoglobin (MCH), mean corpuscular hemoglobin concentration (MCHC), red blood cell distribution width and platelets.
- **Coagulation:** INR (only when increase in LFTs, see Section 6.4), activated partial thromboplastin time and prothrombin time.
- **Clinical chemistry:** glucose, urea, creatinine, uric acid, sodium, potassium, calcium, reflex calcium (free/ionized; only if serum calcium total is elevated), chloride, phosphorus, AST, ALT, GGT, total bilirubin, alkaline phosphatase (ALP, ALP fractions only if ALP is elevated), creatine phosphokinase, lipase, amylase, lactate dehydrogenase, insulin, hemoglobin A1c (HbA1c), albumin, total proteins, triglycerides, cholesterol, high-density lipoprotein (HDL), low-density lipoprotein (LDL), and hsCRP. Homeostatic model assessment of insulin resistance (HOMA-IR, see [Definition of Terms](#)) and HDL/LDL ratio will be derived from clinical chemistry parameters. An estimate of the

ClCr based on the serum creatinine level will be calculated by the central laboratory using the Cockcroft-Gault formula (see [Definition of Terms](#)).

– **Urinalysis:**

Dipstick: pH, glucose, proteins (qualitative), blood, leukocytes, ketones.

Microscopic examination of the sediment for cellular elements (cylinders, erythrocytes, leukocytes), if indicated (when the test strip was positive for blood and/or proteins).

Quantitative urine proteins, only when the test strip was positive for proteins.

Calcium, phosphate, creatinine and N-acetyl- β -D-glucosaminidase (NAG). The urine protein to creatinine ratio will be derived.

– **Serology:**

HBsAg and hepatitis C antibody, and HIV 1 and 2 (at screening). Positive hepatitis and HIV results should be reported by the investigator as required by local law.

– FSH test for females at screening to confirm menopause if applicable

– **Pregnancy test for females:**

serum beta human chorionic gonadotropin at screening, baseline (Visit 1), at Visit 4 (Day 29) and at Visit 5 (Day 43), , or the ED visit, if applicable (all female subjects).

– **QuantiFERON-TB Gold test** to check for latent or active TB (at screening). TB results should be reported by the investigator as required by local law.

– **SARS-CoV-2:**

RT-PCR from a nasal swab sample to check for SARS-CoV-2 infection at screening and RT-PCR from a nasal swab sample and serology testing at baseline, and throughout the study as needed (when SARS-CoV-2 symptoms present).

The clinical laboratory evaluations will be performed at visits specified in the Schedule of Activities in Section 8.11 (see also Section 8.1, “[Timing of Assessments](#)”). Reference ranges will be supplied by the central laboratory. Clinical laboratory values outside the normal range will be flagged and clinical relevance will be assessed by the investigator. Only laboratory test abnormalities judged as clinically significant by the principal investigator should be recorded as AEs.

The details of blood and urine sample handling and shipment instructions will be provided in a separate laboratory manual.

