4.3.4. Definition of Baseline

Baseline is defined as the last available assessment prior to the first intake of IP. For the parameters for which the time of assessment was planned to be collected, if for their assessment on the day of first intake the time is missing, their assessment at time point “PRE-DOSE” (when applicable) will be considered as baseline, otherwise, previous days last available assessment will be selected. For the parameters for which the time of assessment was not planned to be collected, their assessment on the day of first intake of IP will be considered as baseline. If multiple values on the same day qualify as last available assessment, the average of these values will be used in the analysis.

For ECG data assessed in triplicate, baseline is defined as the average (stored without rounding) of the combination of the most complete replicated ECG parameter before first intake of IP and at the same time the closest to it, selecting in the following order:

First consider Day 1, pre-dose:

- Select the average of the last available triplicate ECG parameter on that day;
- If there is no triplicate, select the average of the last available duplicate ECG parameter;
- In the absence of triplicates and duplicates the last available single ECG parameter will become baseline.

If baseline is not yet determined, consider the previous day and repeat the above selection (average of last triplicate, average of last duplicate, last single ECG on that day). Repeat the whole process successively for each previous day(s) as needed until baseline is determined.

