6.3.2.3. Definition of Toxicity Grades

Toxicity grades will only be derived for laboratory tests for which toxicity grades are available.

Toxicity grades will be determined as implemented in the attached table ([Appendix I](#)).

For elevations (H1 to H4), values under the threshold of H1 are reported as 'Grade 0'.

For elevations (L1 to L4), values above the threshold of L1 are reported as 'Grade 0'.

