6.3.2.6. Treatment-Emergent Principle

Toxicity Grades

A post-baseline toxicity grade 1, 2, 3 or 4 is defined as treatment-emergent when higher than the toxicity grade of the baseline result or when there is a change in direction (from H to L or from L to H). If the baseline result is missing, a post-baseline toxicity grade 1, 2, 3 or 4 will be considered as treatment-emergent.

Non-graded Abnormalities

A post-baseline non-graded abnormality class L or H is defined as treatment-emergent when it differs from the abnormality class of the baseline result. If the baseline result is missing, a post-baseline abnormality L or H will be considered as treatment-emergent.

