APPENDIX

APPENDIX I: LABORATORY: TOXICITY GRADING

The following tables contain a list of safety tests with associated gradings. There may be tests in this table that are not measured in this particular study.

Table 1 Gradings for Hematology Parameters

Parameter	L1	L2	L3	L4	H1	H2	H3	H4
Hemoglobin	<LLN	<10 g/dL; <6.2 mmol/L	<8 g/dL; <4.9 mmol/L	NA	>ULN	Increase in >2 g/dL above ULN	Increase in >4 g/dL above ULN	NA
Hematocrit	<LLN	NA	NA	NA	>ULN	NA	NA	NA
Mean corpuscular volume (MCV), mean corpuscular hemoglobin (MCH), mean corpuscular hemoglobin concentration (MCHC)	<LLN	NA	NA	NA	>ULN	NA	NA	NA
Platelet count - (assuming no platelet cluster)	<LLN	<75 x 10 ⁹ /L	<50 x 10 ⁹ /L	<25 x 10 ⁹ / L	>ULN	>600 x 10 ⁹ /L	>1000 x 10 ⁹ /L	NA

Parameter	L1	L2	L3	L4	H1	H2	H3	H4
Leukocytes	<LLN	<3.0 x 10 ⁹ /L	<2.0 x 10 ⁹ /L	<1.0 x 10 ⁹ /L	>ULN	>20.0 x 10 ⁹ /L	>100.0 x 10 ⁹ /L	NA
% Polymorphonuclear Leukocytes + Band Cells	NA	NA	NA	NA	>ULN	≥90%	>95%	NA
Neutrophils	<LLN	<1.5 x 10 ⁹ /L	<1.0 x 10 ⁹ /L	<0.5 x 10 ⁹ /L	NA	NA	NA	NA
Eosinophils	NA	NA	NA	NA	>ULN	>5.0 x 10 ⁹ or eosinophils >5%	NA	NA
Lymphocytes	<LLN	<0.8 x 10 ⁹ /L	<0.5 x 10 ⁹ /L	<0.2 x 10 ⁹ /L	>ULN	>4.0 x 10 ⁹ /L	>20.0 x 10 ⁹ /L	NA

Parameter	L1	L2	L3	L4	H1	H2	H3	H4
Red blood cells	<LLN	NA	NA	NA	>ULN	NA	NA	NA

Table 3 Gradings for Blood Chemistry Parameters

Parameter	L1	L2	L3	L4	H1	H2	H3	H4
Alanine aminotransferase (ALT)	NA	NA	NA	NA	>ULN	>3.0 x ULN	>5.0 x ULN	>8.0 x ULN
Aspartate aminotransferase (AST)	NA	NA	NA	NA	>ULN	>3.0 x ULN	>5.0 x ULN	>8.0 x ULN
Gamma-glutamyl transferase (GGT)	NA	NA	NA	NA	>ULN	>2.5 x ULN	>5.0 x ULN	>20.0 x ULN
Alkaline Phosphatase (total)	NA	NA	NA	NA	>ULN	>2.5 x ULN	>5.0 x ULN	>20.0 x ULN
Lactate dehydrogenase (LDH)	NA	NA	NA	NA	>ULN	NA	NA	NA
Total bilirubin	NA	NA	NA	NA	>ULN	>1.5 x ULN	>3.0 x ULN	>10.0 x ULN
Amylase	NA	NA	NA	NA	>ULN	>1.5 x ULN	>2.0 x ULN	>5.0 x ULN
Lipase	NA	NA	NA	NA	>ULN	>1.5 x ULN	>2.0 x ULN	>5.0 x ULN
Total protein	<LLN	<5.5 g/dL	<5.0 g/dL	NA	NA	NA	NA	NA
Activated partial thromboplastin time (APTT)	NA	NA	NA	NA	>ULN	>1.5 x ULN	>2.5 x ULN	NA

Parameter	L1	L2	L3	L4	H1	H2	H3	H4
Prothrombin time (PT)	NA	NA	NA	NA	≥1.10 x ULN	≥1.25 x ULN	≥1.50 x ULN	≥3.00 x ULN
International normalized ratio (INR)	NA	NA	NA	NA	>1.2 x Baseline	>1.5 x Baseline	>2.5 x Baseline	NA
Creatinine	NA	NA	NA	NA	>ULN	>1.5 x ULN	>3.0 x ULN	>6.0 x ULN

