Any laboratory parameter with treatment-emergent (i.e., worsening from baseline) abnormalities of grade 2 or above (ie, H2/L2 or higher/lower) should be considered a 'marked laboratory abnormality'. Marked laboratory abnormalities should be described in a corresponding section of the CSR as per ICH E3 guidance, section 12.4.2.3.

APPENDIX II: Vital Signs and Electrocardiogram grading**Table 4 Gradings for Vital Signs and Electrocardiogram Parameters**

Parameter	L1	L2	L3	L4	H1	H2	H3	H4
Systolic blood pressure (mmHg)	<90	<60	NA	NA	NA	≥140	≥160	≥180
Diastolic blood pressure (mmHg)	<60	<45	NA	NA	NA	≥90	≥100	≥120
Heart rate (bpm)	<60	<50	<40	NA	>100	>115	>130	NA
Body temperature (°C)	NA	<35	NA	NA	>38	NA	NA	NA
Respiratory rate (breaths per minute)	<12	NA	NA	NA	>20	NA	NA	NA
O ₂ saturation (%)	<95	<90	NA	NA	NA	NA	NA	NA
Weight	≥7% decrease from baseline	NA	NA	NA	≥7% increase from baseline	NA	NA	NA
QTc interval on ECG (ms)	NA	NA	NA	NA	>450	>480	>500	NA
QTc change from baseline (ms)	NA	NA	NA	NA	NA	>30	>60	NA
PR interval on ECG (ms)	<110	NA	NA	NA	>200	NA	NA	NA

Parameter	L1	L2	L3	L4	H1	H2	H3	H4
QRS complex on ECG (ms)	<60	NA	NA	NA	>120	NA	NA	NA

Source: FRM-MED-005/006, valid on 08JUL2020.

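### The SAP grades INR only against baseline, but the protocol measures INR only once liver tests rise, so an on-treatment INR will normally have no toxicity grade

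*Protocol*

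**What the plan says.** Protocol 8.5.2 lists the coagulation tests as "INR (only when increase in LFTs, see Section 6.4), activated partial thromboplastin time and prothrombin time". The restriction applies to INR alone; the other two tests carry none. The cross-reference is to section 6.4, which deals with liver enzyme increases during treatment. The schedule of activities shows clinical safety blood samples at screening and Visit 1, but nothing in the protocol assigns an INR to a pre-dose visit.

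On grading, SAP 6.3.2.3 states: "Toxicity grades will be determined as implemented in the attached table". In Appendix I the INR row reads ">1.2 x Baseline" for H1, ">1.5 x Baseline" for H2 and ">2.5 x Baseline" for H3. H4 is not applicable, and the row has no ULN-based or absolute cut-off.

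On baseline, SAP 4.3.4 states: "Baseline is defined as the last available assessment prior to the first intake of IP". SAP 4.3.6.2 imputes no missing results unless specified, and nothing is specified for a missing laboratory baseline. SAP 6.3.2.6 adds: "If the baseline result is missing, a post-baseline toxicity grade 1, 2, 3 or 4 will be considered as treatment-emergent". The closing paragraph of Appendix I says that any parameter with a treatment-emergent abnormality of grade 2 or above "should be considered a 'marked laboratory abnormality" and is to be described in the clinical study report.

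**The concern.** The protocol makes INR an event-triggered test, while the SAP grades it on a scale that presupposes a routine pre-dose value. Both choices are reasonable alone, but together they leave the grading rule without its denominator in most of the subjects in whom INR will be measured.

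INR matters here because INR above 1.5 is one of the protocol's own signs of liver damage (sections 6.4 and 11.1.5, Appendix 8). Appendix 8 also asks for INR two to three times a week under close observation. Those values would normally not reach the toxicity-grade tables of SAP 6.3.2.9 or the marked-abnormality description in the report. SAP 6.3.2.8 (Hepatotoxicity) does not use INR and so does not fill the gap.

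**Working it through.** The documents state no figure to reproduce. The check is to follow the grading rule through and see whether it returns a result.

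1. **Baseline.** For a subject with normal liver tests at screening and Visit 1, protocol 8.5.2 does not call for INR. There is then no pre-dose assessment for SAP 4.3.4 to select, and SAP 4.3.6.2 does not impute one.
2. **Grade.** With R = on-treatment INR / baseline INR, Appendix I gives H3 if R > 2.5, H2 if R > 1.5, H1 if R > 1.2, and otherwise Grade 0. Without a baseline, R is undefined at every INR value.
3. **Missing-baseline rule.** SAP 6.3.2.6 decides whether an existing grade 1 to 4 is treatment-emergent. It does not create a grade. It works for rows tied to ULN, such as prothrombin time, but not for a row tied to baseline.
4. **Worst case.** SAP 6.3.2.7 sets the toxicity grade to missing if any record is missing.
5. **Marked abnormality.** This needs grade 2 or above, so it cannot be reached.

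The documents give no INR values. For illustration, assume baselines of 0.9 to 1.2 and four on-treatment values:

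| On-treatment INR | No baseline | Baseline 0.9 | Baseline 1.0 | Baseline 1.1 | Baseline 1.2 |
|---|---|---|---|---|---|
| 1.3 | no grade | R 1.44, H1 | R 1.30, H1 | R 1.18, Grade 0 | R 1.08, Grade 0 |
| 1.6 | no grade | R 1.78, H2 | R 1.60, H2 | R 1.45, H1 | R 1.33, H1 |
| 2.0 | no grade | R 2.22, H2 | R 2.00, H2 | R 1.82, H2 | R 1.67, H2 |
| 2.6 | no grade | R 2.89, H3 | R 2.60, H3 | R 2.36, H2 | R 2.17, H2 |

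An INR of 2.0 would be H2, and so marked, at every assumed baseline. Under the plan as written it has no grade. The 1.6 row also shows that the SAP scale and the protocol's criterion differ: 1.6 exceeds the absolute 1.5, yet it is H2 or H1 depending on the baseline.

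**The case against.** The strongest reply is that little safety information is lost, and much of it stands.

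- **A raised INR remains visible.** SAP 6.3.2.4 classes laboratory results as low, normal or high against the normal range, which needs no baseline. Under 6.3.2.6 a high value with a missing baseline is treatment-emergent, and 6.3.2.9 tabulates it. This holds for central-laboratory results; SAP 6.3.2.1 only lists local ones.
- **Prothrombin time is graded.** It has no liver-test trigger, and Appendix I grades it H1 to H4 against ULN. It would often show the same disturbance. The cover is incomplete, because the close-observation list in Appendix 8 names INR but not prothrombin time, and the documents do not give what is needed to translate an INR into a prothrombin-time grade.
- **Liver rules do not use the SAP grade.** The discontinuation and serious-adverse-event criteria use an absolute INR above 1.5. AST or ALT at or above 3 times ULN with such an INR is reportable as serious whatever the grade.
- **Appendix I is generic.** It warns that it may list tests not measured in this study. That does not excuse the INR row, since protocol 8.5.2 names INR as a study test.
- **A pre-dose INR may exist.** Liver tests could already be raised before dosing, or an unscheduled test could be done (protocol 8.5). Hence the qualifier normally.

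A reader might infer that a raised INR in a liver case would go unreported, or that stopping and serious-event reporting are weakened. The first and third bullets show that the documents do not support either reading. A reader might also infer that all 25 planned subjects are affected. Most of them may lack a baseline INR, but a subject whose liver tests never rise has no on-treatment INR to grade and loses nothing.

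What survives is that a high flag carries no severity, and the marked-abnormality definition is written in grades.

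**Conclusion.** The point holds in limited form. For a subject with no pre-dose INR, the INR row of Appendix I cannot return a grade at any value. What is lost is the INR toxicity grade, its place in the graded shift and worst-case tables, and the marked-abnormality label.

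The affected group is subjects with an on-treatment liver-test rise, an INR drawn and no pre-dose INR; a grade of 1 or above is lost only if that INR is also raised. The documents give no expected number in this 25-subject, six-week study, and it may be small. The primary analysis, the adverse-event endpoint and the protocol's liver criteria are not affected.

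The conclusion assumes that sites follow 8.5.2 as written and that no separate laboratory instruction adds a baseline INR. It is a safety-reporting rule that does not work for the subjects in whom the test is planned, and it is worth correcting because the correction is cheap.

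**What to change.** Either of two changes is enough.

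1. **SAP route (simplest).** Before database lock, change the Appendix I INR row to a basis that needs no baseline, at least when baseline INR is missing. Multiples of ULN are one example, already used for prothrombin time and APTT; the sponsor should set the multiples. A grade could then be derived, and the existing missing-baseline rule in 6.3.2.6 would make it treatment-emergent, so the frequency table and the marked-abnormality rule would work. The shift table should show such subjects with a missing baseline category. The cost is one table row and a line in the SAP version history.
2. **Sampling route.** Have the central laboratory report one baseline INR from the Visit 1 coagulation sample. INR is calculated from prothrombin time, so no extra blood is needed. The cost is a small wording change to the protocol and laboratory manual, with the ethics submission that an amendment needs. It helps only subjects enrolled afterwards, or those whose earlier results the laboratory can still convert.

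The liver-test trigger need not be deleted, and INR need not be run at every visit; grading needs one pre-dose value. Whichever route is taken, the SAP should state how its INR grades relate to the protocol's absolute INR criterion, so that the two scales are not read as one.
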